8.2.2. Secondary Endpoints

The secondary efficacy endpoints for the study are:

• Duration of COVID-19 associated symptoms from start of study treatment (Day 0) based on self-assessment using daily symptom diary.

Duration is defined as number of days when any symptoms scored as

- moderate or severe is defined as number of days are still scored as moderate or severe (i.e., not mild or absent) through Day 56, or
- mild or absent at study entry are scored as mild or worse (i.e., not absent) through Day 56.
- Number of symptom-free days of COVID-19 associated symptoms that were present at the start of study treatment (Day 0) based on self-assessment using daily symptom diary.
 - Symptom-free days are defined as number of days when any symptoms scored as mild, moderate or severe at baseline are scored as absent (or none) through Day 56.

CONFIDENTIAL Page 68 of 101

• Progression (or worsening) of COVID-19-associated symptoms through Day 56 compared to baseline.

Progression or symptom worsening is defined as number of days when any symptoms scored as

- moderate at baseline are scored as severe through Day 56.
- mild at baseline are scored as moderate or severe through Day 56.
- absent at baseline are scored as mild, moderate or worse through Day 56.
- Change from baseline in PROMIS® Fatigue Score at Days 28 and 56.
- Change from baseline in PROMIS® Cognitive Function Score at Days 28 and 56.
- Change from baseline in PROMIS® Sleep Disturbance Score at Days 28 and 56.
- Incidence of hospitalization during the treatment phase
- Duration (days) of hospitalization during the treatment phase

8.2.3. Exploratory Outcome Measures (Endpoints)

- Change from baseline in pulse oxygen saturation (SpO2) at Day 7, 14, 21, 28, 35, 42, 49, and 56.
- Change from baseline in serum cytokine and chemokine levels on Days 28 and 56.
- Change from baseline in CD4+ and CD8+ T cell count on Days 28 and 56.
- Change from baseline in Transgrowth factor beta 1 (TGF beta1) on Days 28 and 56.
- Change from baseline in CRP on Days 28and 56.
- Change from baseline in CCR5 receptor occupancy on Days 28 and 56.
- To explore biomarkers that may predict and/or act as pharmacodynamic indicators of pharmacologic activity of leronlimab.
- Evaluation of Global Health Assessment at Day 56.

8.2.4. Safety Measures

Safety will be assessed using:

- Incidence of treatment-related adverse events (TEAEs)
- Incidence and severity of treatment-emergent adverse events (TEAEs)
- Incidence of serious adverse events (SAEs)
- Incidence of TEAEs and SAEs leading to discontinuation of study medication.
- Changes in blood chemistry, hematology and coagulation parameter results

CONFIDENTIAL Page 69 of 101

- Changes in vital signs including temperature, pulse, respiratory rate, systolic and diastolic blood pressure
- Changes in physical examination results
- Changes in electrocardiogram (ECG) results

8.3. SAMPLE SIZE DETERMINATION AND RATIONALE

A total of 50 subjects will be randomized 1:1 in this study. The sample size is based on clinical judgment. No statistical power calculation is used to establish the sample size for this exploratory study.

8.4. RANDOMIZATION

This is a multi-center randomized clinical trial. An individual, independent of the clinical trial team, will develop the randomization schedules. The actual randomization assignment will be made through an Interactive Web Based Response System (IWRS) called WebView[®]. Subjects who have provided written informed consent and have met all the inclusion criteria and none of the exclusion criteria will be randomized to one of the treatment groups.

8.5. STRATIFICATION

Randomization will be stratified by symptom duration (defined as time from first reported symptom onset to the time of randomization) of 12 - 24 weeks or > 24 weeks.

8.6. BLINDING

All subjects, Investigators and their staff (except unblinded pharmacist or designated site staff), and all Sponsor/CRO personnel involved in the management of the study will be blinded to treatment assignments.

The Amarex Information Technology department will be unblinded to treatment. As noted above, the Amarex Technology department is not otherwise involved with the study.

Treatment unblinding for the study will occur after all clinical data have been received, data inconsistencies have been resolved, and the database is locked, except for safety reasons on a case-by-case basis (i.e., emergency unblinding).

The process for emergency unblinding will be outlined in detail in the Randomization Plan. In addition, any subject that is unblinded for any reason will be identified and discussed in the final clinical study report.

8.7. TIME TO UNBLINDING

8.7.1. Emergency Unblinding

CONFIDENTIAL Page 70 of 101

Breaking the blind prematurely will be allowed only if the subject's well-being requires knowledge of the subject's treatment allocation. Every attempt will be made to maintain the blind throughout the study.

In the event of an urgent safety issue where the randomized treatment of a subject is necessary to manage and treat the affected study subject (e.g., unblinding subjects because of SAEs that meet "expedited criteria" and requires reporting to FDA and other global regulatory authority), the Investigator will contact the Medical Monitor. The Medical Monitor, in consultation with sponsor, will make a decision to unblind. If the decision has been made to unblind, a prompt written notification will be provided to the Investigator. The reason for unblinding must be recorded; however the investigator must not record the subject's treatment assignment in study documentation and must not reveal the subject's treatment assignment to the clinical monitor.

If reporting of an adverse event is to be performed unblinded as per regulatory authority guidelines, study-unrelated personnel will unblind the individual subject's treatment group and will perform the unblinded reporting. No treatment group information would be shared with study personnel.

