2.8 Time to Unblinding

2.8.1 Emergency Unblinding

Breaking the blind prematurely will be allowed only if the subject's well-being requires knowledge of the subject's treatment allocation. Every attempt will be made to maintain the blind throughout the study.

In the event of an urgent safety issue where the randomized treatment of a subject is necessary to manage and treat the affected study subject (e.g., unblinding subjects because of SAEs that meet "expedited criteria" and requires reporting to FDA and other global regulatory authority), the Investigator will contact the Medical Monitor. The Medical Monitor, in consultation with sponsor, will make a decision to unblind. If the decision has been made to unblind, a prompt written notification will be provided to the Investigator. The reason for unblinding must be recorded; however the investigator must not record the subject's treatment assignment in study documentation and must not reveal the subject's treatment assignment to the clinical monitor.

If reporting of an adverse event is to be performed unblinded as per regulatory authority guidelines, study-unrelated personnel will unblind the individual subject's treatment group and will perform the unblinded reporting. No treatment group information would be shared with study personnel.

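### Protocol 8.7.1 and SAP 2.8.1 give an SAE that needs expedited reporting two contradictory unblinding routes, one of which can needlessly unblind the investigator

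*Combined protocol and SAP*

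**What the plan says.** Protocol 8.7.1 has three paragraphs, and SAP 2.8.1 repeats them.

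- **First paragraph, the general condition:** "Breaking the blind prematurely will be allowed only if the subject's well-being requires knowledge of the subject's treatment allocation".
- **Second paragraph, the care route:** this covers an urgent safety issue in which the allocation is needed to treat the subject. Its example is an SAE that meets expedited criteria "and requires reporting to FDA and other global regulatory authority), the Investigator will contact the Medical Monitor". On the decision it says: "The Medical Monitor, in consultation with sponsor, will make a decision to unblind". Then: "If the decision has been made to unblind, a prompt written notification will be provided to the Investigator". The investigator may not write the assignment into study documents or disclose it to the clinical monitor.
- **Third paragraph, the reporting route:** where regulatory guidelines call for an unblinded report, people unconnected with the study break the code and file it. "No treatment group information would be shared with study personnel".

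Protocol 8.6 and SAP 2.7 leave the detailed emergency process to a Randomization Plan. They also require every unblinded subject to be identified and discussed in the study report. Site staff are blinded "except unblinded pharmacist or designated site staff".

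**The concern.** A duty to report to a regulator is not a treatment need of the subject. By offering expedited reporting as an example of the care route, the second paragraph goes against the first and overlaps the third. A site or Medical Monitor who follows the example ends with the investigator informed. One who follows the third paragraph ends with nobody in the study informed.

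What is at stake is blinded causality assessment. Protocol 9.2.3 makes the investigator responsible for relatedness, and stopping rules 1 to 3 in Protocol 5.2 turn on relatedness as judged by the treating investigator. Protocol Section 12 provides no data safety monitoring committee, so no independent committee would re-read those judgements. The third paragraph itself shows that reporting can be done without telling the investigator.

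A secondary matter is the true emergency. The care route passes through a contact, a decision taken with consultation, and a written notice. The two documents state no time limit and no fallback.

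**Working it through.** No formula or sample-size figure bears on this, so the check sets the paragraphs side by side.

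| | Second paragraph (care route) | Third paragraph (reporting route) |
|---|---|---|
| Trigger | Allocation needed to treat the subject | Adverse event must be reported unblinded |
| Example given | SAE that "requires reporting to FDA and other global regulatory authority" | None |
| Who decides or unblinds | Medical Monitor, after consulting the sponsor | People unconnected with the study |
| Who is told | The investigator, in writing | Nobody among study personnel |

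That the investigator learns the allocation on the care route is an inference, but a firm one: a ban on recording or disclosing the assignment presupposes knowing it.

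Three cases then test the text.

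1. **Care depends on the allocation; no unblinded report is due.** The first paragraph permits unblinding and only the second applies. There is no conflict.
2. **Care depends on the allocation and an unblinded report is due.** The care route informs the investigator for treatment, and the reporting route can run separately. The two can coexist if each is confined to its own purpose.
3. **An unblinded expedited report is due; care does not depend on the allocation.** The first paragraph does not permit early unblinding at the site. The second paragraph's condition is not met, but its example describes this event. The third paragraph also describes it. One reading informs the investigator and the other informs nobody in the study.

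Case 3 is the contradiction. The SAP carries the same wording, so it does not settle which route applies.

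For the emergency itself:

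- **Authority.** The investigator's stated part is limited: "the Investigator will contact the Medical Monitor". No section of either document lets the investigator decide or break the code.
- **Timing.** The notice is described as prompt, without a figure. The 24 hours in Protocol 9.4 is for sending SAE reports to the Medical Monitor and does not limit the unblinding decision.
- **Where the allocation is held.** Assignments are made through the web system (Protocol 8.4), and an unblinded pharmacist or designee prepares the syringes (Protocol 6.1.3 and 8.6). The information therefore exists close to the investigator.

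**The case against.** The best reply is that the paragraphs have different triggers. The second applies only when the allocation is needed to treat the subject, its example sits inside that condition, and the opening sentence governs both. A case that needs only reporting fails the condition and goes to the third paragraph. In addition, nobody is unblinded on the care route until the Medical Monitor decides. This is probably what the authors meant, but it works only if the example is ignored, because the example gives the expedited, reportable SAE as the reason for unblinding. The objection limits the harm to a drafting conflict that needs a decision before it takes effect; it does not remove the conflict.

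On emergency access the reply is stronger. Protocol and SAP agree on who decides, so this is a design criticism and not an inconsistency. Timing and access may be set in the Randomization Plan, which was not available. The supportable statement is that the protocol and SAP do not give them.

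A reader might infer more than the documents support:

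- **That urgent care is delayed.** No delay is documented. The route can delay access, and that is all the text shows.
- **That two approvals are needed.** There is one decision-maker, who consults the sponsor. Consultation is not approval.
- **That the investigator counts stopping-rule events.** The treating investigator judges relatedness. Under Protocol 5.2 the Medical Monitor and Lead Principal Investigator review the data, and the Medical Monitor and sponsor may agree to let the study proceed.
- **That the sponsor's earlier mild-to-moderate COVID-19 trial (Protocol 1.4.2.18) bounds the number affected.** Its SAEs were (5 + 6)/(56 + 28) = 11/84 = 13.1% of subjects, and 0.131 × 50 = 6.5. That is a pooled point estimate from acute disease with a Day 14 primary endpoint. This trial enrols people with symptoms beyond 12 weeks and follows them to Day 84. The figure bounds nothing here, and the documents do not say how many SAEs would meet expedited criteria.

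**Conclusion.** The internal contradiction stands and is wrong as written in both documents. For an SAE that needs unblinded expedited reporting but whose care does not depend on the allocation, the text supports two routes with opposite effects on the blind, and one of them can needlessly unblind the person judging causality. This rests on two readings: that the example is meant to be followed, and that the written notice conveys the allocation.

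The emergency-access matter is secondary, an improvement in design. It rests on the protocol and SAP alone and could be partly or wholly met by the Randomization Plan.

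The number of subjects affected cannot be estimated. It is limited to SAEs that meet expedited criteria and are sent down the care route. Nothing here supports inferring that the patient-rated primary endpoint is compromised, since neither route provides for telling the subject.

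**What to change.** **Correction.** In the second paragraph of Protocol 8.7.1 and of SAP 2.8.1, delete the expedited-reporting example. Unblinding done only for regulatory reporting then follows the third paragraph, and the section agrees with its own opening sentence. The cost is one parenthesis in each document. No analysis, visit or sample size changes.

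**Cheap improvement.** State in Protocol 8.7.1, SAP 2.8.1 and the Randomization Plan that an investigator who judges the allocation necessary for immediate care can obtain it without waiting for the Medical Monitor's decision, recording the reason and informing the Medical Monitor. First check whether the Plan already covers timing or access. The cost is wording and a means of access; the documents do not describe whether the web system already offers a code break. The downside is a small risk of an unnecessary code break, which would be visible because Protocol 8.6 already requires each unblinded subject to be identified and discussed in the study report.

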8.7.2. Final Analysis

Treatment unblinding and release of the randomization codes of the investigational product assignments for the study will occur immediately following database lock when all randomized subjects have completed the study or discontinued from the study and after all clinical data have been received and data inconsistencies have been resolved.

8.8. INTERIM ANALYSIS

There will be no interim analysis performed in this study

8.9. GENERAL STATISTICAL CONSIDERATIONS

All collected study data will be presented in subject data listings. Statistical analyses will be performed using SAS® for Windows, version 9.4 or later. Descriptive statistics (n, mean, standard deviation, median, minimum and maximum) will be presented for continuous variables. Frequencies and percentages will be presented for categorical variables.

8.9.1. Analysis Populations

8.9.1.1. Modified Intent-to-Treat Population

The **Modified Intent-to-Treat (mITT) population** is defined as the set of subjects who have received at least one dose of study treatment (leronlimab or placebo). This population will be used as the primary analysis population for analysis of the primary and secondary efficacy endpoints.

8.9.1.2. PP Population

CONFIDENTIAL Page 71 of 101

The **Per Protocol** (**PP**) **population** is defined as the set of subjects who meet the ITT Population requirements and are not associated with any major protocol violations. This population will be identified before the database lock. This population will be used as the supportive analysis population for analysis of the primary and secondary efficacy endpoints.

8.9.1.3. Safety Population

The **Safety Population** will include all subjects who have received one dose of study treatment (leronlimab or placebo). This population will be used for the analysis of safety parameters or measurements.

8.9.2. Covariates

For efficacy analyses important prognostic factors that need adjustment will be specified in the Statistical Analysis Plan (SAP) for the study

8.9.3. Missing Data

Every effort will be made to obtain required data at each scheduled evaluation from all subjects who have been randomized to minimize missing data. However, in the event when there is missing data the following imputation methods will be used.

For efficacy evaluations, multiple imputation methods will be used to handle missing data. This imputation method is a robust method to impute missing measurements. The imputation will be carried out in SAS version 9.4 or later using PROC MI. Each imputation model will include the stratification factor as a covariate in the model. The details of multiple imputation will be included in the statistical analysis plan.

8.10. Analysis Methods

A Statistical Analysis Plan (SAP) will be developed and approved before the database is locked. The SAP will present the detailed statistical methodology to be used in analyzing the data from this trial.

8.10.1. Subject Disposition

The disposition of all subjects who signed an ICF will be provided. The number of subjects screened, screen failed, randomized, received at least one treatment, completed, and discontinued during the study, as well as the reasons for all discontinuations will be summarized by treatment group. Disposition and reason for study discontinuation will also be provided as a by-subject listing.

8.10.2. Demographic and Baseline Characteristics

Demographics and baseline characteristics including medical history, will be summarized by treatment group using appropriate descriptive statistics.

CONFIDENTIAL Page 72 of 101

8.10.3. Concomitant Medications/Therapies

Concomitant medications/therapies will be summarized separately for the Safety population. All prior and concomitant medications recorded in the case report form will be coded to matching Anatomic Therapeutic Classification codes using the most recent version of the WHO Drug Dictionary. Descriptive summaries by treatment group will be prepared using the coded term. All concomitant medications/therapies recorded in the case report form will be listed.

8.10.4. Efficacy Analyses

Primary Analysis

The mITT population will be the primary population for the analysis of the efficacy endpoints of the study.

Primary Endpoint

The primary endpoint for this study is the change from baseline in Fatigue Severity Score at Day 28.

Secondary Endpoints

To maintain the trial-wise Type I error rate at 0.05, a closed test procedure will be used for the secondary endpoints. The order of the secondary endpoints will be prospectively specified in the SAP.

Analysis of the secondary and exploratory endpoints will be summarized according to the variable type:

- Continuous data summaries will include:
 - o If the Normality assumption is met, Analysis of Covariance (ANCOVA) would be used.
 - If the Normality assumption is not met, a non-parametric method or a rank ANCOVA analysis i.e., an ANCOVA analysis on rank-transformed data will be used.
- Categorical data summaries will be based on Logit model will be used.
- Time-dependent data: Cox proportional hazards model will be used to analyze time dependent data and to depict the time to event data.

8.10.5. Supportive Analysis

To assess the consistency of the Primary Analysis results, supportive analysis will be conducted using the modified Intent to Treat (mITT) and Per Protocol (PP) populations. Statistical methodology for the supportive analyses will be the same as that of the primary analysis, with the exception of the analysis population used.

8.10.6. Subgroup Analysis

CONFIDENTIAL Page 73 of 101

Subgroup analyses will be conducted for the predefined stratification factors (Section 8.5) for the study. Additional exploratory subgroup analysis will be conducted using the baseline clinical characteristics and laboratory parameters. The details will be prospectively specified in the SAP.

Safety Summaries

8.10.6.1. Adverse Events

Adverse events will be coded using the most recent version of Medical Dictionary for Regulatory Activities (MedDRA). Treatment Emergent AE's (TEAE) are defined as events with an onset on or after the first treatment. TEAEs will be summarized by System Organ Class and preferred term by treatment group. The following TEAE summaries will be provided:

- Overall (i.e., regardless of severity or relationship to treatment);
- By intensity (mild, moderate, severe, life threatening or death);
- By causality (definitely, probably, possibly, unlikely or unrelated);
- By impact on study treatment (dose increased, dose not changed, dose rate reduced, dose reduced, drug interrupted, drug withdrawn, not applicable, or unknown).

In addition, separate summaries of serious adverse events, and adverse events resulting in discontinuation of study treatment will be presented.

8.10.6.2. Clinical Laboratory Data

All laboratory values will be listed. Laboratory measurements will also be summarized by treatment group and presented by time point.

8.10.6.3. ECG

All ECG values will be listed. ECG measurements will also be summarized by treatment group and presented by time point.

8.10.6.4. Vital Signs

All vital sign findings will be listed and/or summarized by treatment group.

8.10.6.5. Physical Examination

All physical examination findings will be listed and/or summarized by treatment group.

CONFIDENTIAL Page 74 of 101

9. ADVERSE EVENTS (DEFINITIONS AND REPORTING)

The Investigator is responsible for the detection and documentation of events meeting the criteria and definition of an AE or SAE, as provided in this protocol. During the study when there is a safety evaluation, the Investigator or site staff will be responsible for detecting, documenting and reporting AEs and SAEs as detailed in this Section of the protocol.

